2.3.2 Secondary Objectives

Group A

- 1. To compare the week 12 geometric mean titers (GMT) of a two-dose regimen of HEPLISAV-B (Arm 1) versus the week 28 GMT of a standard three-dose regimen of ENGERIX-B (Arm 3) in HBV vaccine-experienced participants living with HIV.
- To compare the week 28 GMT of a three-dose regimen of HEPLISAV-B (Arm 2) versus a standard three-dose regimen of ENGERIX-B (Arm 3) in HBV vaccine-experienced participants living with HIV.
- 3. To compare the SPR and GMT 4, 8, 24, and 48 weeks after last vaccination of a two-dose regimen of HEPLISAV-B (Arm 1) versus a standard three-dose regimen of ENGERIX-B (Arm 3) in HBV vaccine-experienced participants living with HIV.

- 4. To compare the SPR and GMT 8, 24, and 48 weeks after last vaccination of a three-dose regimen of HEPLISAV-B (Arm 2) versus a standard three-dose regimen of ENGERIX-B (Arm 3) in HBV vaccine-experienced participants living with HIV.
- 5. To compare the SPR and GMT 4, 8, 24 and 48 weeks after last vaccination of a two-dose regimen of HEPLISAV-B (Arm 1) versus a three-dose regimen of HEPLISAV-B (Arm 2) in HBV vaccine-experienced participants living with HIV.
- 6. To assess SPR and GMT at weeks 4, 8, 12, and 24 between HEPLISAV-B (Arms 1 and 2 combined) and ENGERIX-B (Arm 3) in HBV vaccine-experienced participants living with HIV (Group A).
- To describe incidence of Grade≥2 AEs within 4 weeks of each injection in each study arm.
- 8. To assess host characteristics associated with vaccine response.
- 9. To compare SPR and GMT at week 72 between HEPLISAV-B two-dose (Arm 1) and three-dose arms (Arm 2).

Group B

- 1. To determine the week 28 GMT of a three-dose regimen of HEPLISAV-B in HBV vaccine-naïve participants living with HIV.
- 2. To determine the SPR and GMT of a three-dose regimen of HEPLISAV-B at weeks 32, 48, and 72 in HBV vaccine-naïve participants living with HIV.
- 3. To determine the SPR and GMT of a three-dose regimen of HEPLISAV-B at weeks 4, 8, 12, and 24 in HBV vaccine-naïve participants living with HIV.
- 4. To describe incidence of Grade ≥2 AEs within 4 weeks of each injection.
- 5. To assess host characteristics associated with vaccine response.

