5.2 Analysis Approaches

5.2.1 Group A Primary:

- For each of the two primary objectives on vaccine response, the primary outcome measure on the SPR will be analyzed as a binary variable.
- A score-based approach similar to the Wilson method for a SPR proportion difference will be used to estimate a stratified confidence interval, known as Newcombe method (Yan

- and Su, 2010). Four strata will be defined by sex at birth and screening diabetes status, and the strata will use Mantel-Haenszel weights (Mantel and Haenszel. 1959).
- Non-inferiority comparison between Arms 1 and 3: For the final analysis, a two-sided 97.5% confidence interval will be provided for the estimated proportion difference between Arm 1 and Arm 3 (Arm 3 minus Arm 1). If the resulting confidence interval lies entirely below the non-inferiority margin of 10%, then non-inferiority of Arm 1 compared to Arm 3 (control) will be concluded. Superiority of Arm 1 compared to Arm 3 will be concluded if the confidence interval lies entirely below zero.
- Superiority comparison between Arms 2 and 3: For the final analysis, a two-sided 97.5% stratified confidence interval will be provided for the proportion difference between Arm 2 and Arm 3 (Arm 2 minus Arm 3). A repeated confidence interval approach according to the realized Lan and DeMets implementation of the O'Brien-Fleming sequential stopping boundary that accounts for the repeated analyses due to interim efficacy monitoring will be provided. If the resulting confidence interval lies entirely above zero, then superiority of Arm 2 compared to Arm 3 (control) will be concluded.
- To address the study objectives on safety, the proportion of participants with AEs will be summarized with a two-sided 95% confidence interval in each study arm using the Wilson method, across stratification factors.

5.2.2 Group A Secondary:

- The secondary analyses on SPR will be conducted using a two-sided type I error rate of 2.5% without further correction for multiple analyses. This type I error was chosen to provide confidence intervals of widths comparable to the primary outcome analyses.
- The secondary objectives on the SPR comparisons will be addressed using the following analysis approach. A two-sided 97.5% confidence interval around the difference in proportions will be calculated using the Newcombe method. These will also be stratified confidence intervals, similar to the primary analysis approach.

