- For the secondary objectives on the analysis of the antibody titer as a continuous measure, two-sided type I error rate of 5% without correction for multiple analyses will be used. The geometric mean titer will be calculated for each analysis group (study arm or combined study arms, depending on the objective) and compared using a t-test. A two-sided 95% confidence interval around the difference in the geometric means will be calculated assuming t-distribution of log₁₀-transformed antibody titer. The confidence intervals will be provided across stratification factors and within stratum.
- o For the secondary objective (e.g. Objective 6) where Arms 1 and 2 are combined to compare to Arm 3 (control), the analysis will occur if the directions in the outcome differences between Arm 1 and Arm 3 and between Arm 2 and Arm 3 are the same. Otherwise, the analysis where Arms 1 and 2 are combined will not be interpretable.
- To address the objective on post-injection AEs, the proportion of participants with events will be summarized with a two-sided 95% confidence interval in each study arm using the Wilson method.
- Logistic regression models will be developed to assess host characteristic factors
 associated with vaccine response defined by the primary outcome on the SPR. The
 factors include age, sex, race, diabetes, body mass index (BMI), CD4+ T-cell count, and
 smoking status at baseline. Each factor will be considered in a separate model that only

controls for the study arm as a covariate, and a p-value <0.20 will determine entry into a full model. Then all-subsets variable selection approach will be used with a p-value cutoff of 0.05 as a criterion to retain in the final model, while keeping the study arm in the model throughout the procedure.

5.2.3 Group B Primary:

- The primary outcome on the SPR at 4 weeks after the vaccination series will be assessed by estimating the proportion of participants who achieve SPR. A two-sided 95% confidence interval around the observed SPR proportion will be provided using the Wilson score method for binomial variables. If the confidence interval lies above 55%, then it will be concluded that the SPR proportion is greater than 55%.
- To address the primary objective on safety, the proportion of participants with AEs will be summarized with a two-sided 95% confidence interval using the Wilson method.

5.2.4 Group B Secondary:

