- Each secondary analysis will be conducted using a two-sided type I error rate of 5% without correction for multiple analyses.
- To address the secondary objectives on the SPR at additional study weeks, a two-sided 95% confidence interval around the observed SPR proportion will be provided for each, using the Wilson score method for binomial variables.
- To address the secondary objectives related to antibody titer as a continuous measure, the GMT will be calculated with two-sided 95% confidence intervals, assuming tdistribution of log₁₀-transformed antibody titer.
- To address the study objective on post-injection AEs, the proportion of participants with events will be summarized with a two-sided 95% confidence interval using the Wilson method.
- Logistic regression models will be developed to assess host characteristic factors associated with vaccine response defined by the primary outcome on the SPR. The approach described for Group A (Section 5.2.2 above) will also be used for Group B.

References:

Yan, X., & Su, X. G. (2010). Stratified Wilson and Newcombe confidence intervals for multiple binomial proportions. Statistics in Biopharmaceutical Research, 2(3), 329-335.

Mantel, N., and Haenszel, W. (1959). "Statistical Aspects of Analysis of Data from Retrospective Studies of Disease." Journal of the National Cancer Institute 22:719–748.

6 Report Contents

Additional details will be provided in an AIP. In addition to results for primary and secondary outcome measures, baseline characteristics and study status are reported to ClinicalTrials.gov.

- 1. CONSORT Diagram
- 2. Study history
 - a. A summary of changes to and clarifications of the protocol
 - b. A brief summary of the DSMB reviews
- Study entry
 - a. Screening: Number of participants screened for the study
 - b. Accrual: Tables of accrual by month and by site
- 4. Baseline characteristics
 - a. Demographics: age, sex, gender, IV drug use, race, ethnicity, country
 - b. Weight and BMI
 - c. Plasma HIV-1 RNA level, CD4+ and CD8+ T-cell count and percent
 - d. ARV regimen
 - e. Smoking status
 - f. Diabetes status
- 5. Study status
 - a. Listing of premature study discontinuation with reasons. For premature discontinuations, the number of weeks on study will be provided.
- 6. Study treatment status

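### Group A GMT contrasts: no stratum-adjusted overall comparison is stated, and the planned interval estimates a ratio of GMTs where the SAP names a difference (low priority)

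*SAP*

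**What the plan says.** SAP 2.1.1 randomises Group A 1:1:1, stratified by sex at birth and diabetes status. SAP 5.2.1 carries those four strata into the final SPR analysis through a stratified Newcombe interval with Mantel-Haenszel weights. SAP 5.2.2 does the same for the secondary SPR comparisons: "These will also be stratified confidence intervals, similar to the primary analysis approach".

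The GMT part of 5.2.2 is different. GMTs are calculated for each analysis group ("study arm or combined study arms, depending on the objective) and compared using a t-test"). The interval is described thus: "A two-sided 95% confidence interval around the difference in the geometric means will be calculated assuming t-distribution of" log10-transformed titer. On the strata it says only: "The confidence intervals will be provided across stratification factors and within stratum". It gives no weights, combining rule or model.

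The target quantity is called a difference throughout: in the population-level summaries of 4.5.1, 4.5.2 and 4.5.4, in 5.2.2, and in Section 6 items 11 and 13. The text supplied mentions no ratio of GMTs, no back-transformation rule and no direction of contrast for GMT. The primary SPR contrasts do have stated directions (Arm 3 minus Arm 1, Arm 2 minus Arm 3).

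**The concern.** Two things do not fit together.

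First, the analysis of titer appears not to use the strata by which the trial randomises. When allocation is balanced within strata, the between-stratum part of the titer variance does not contribute to the error of the arm difference. A pooled t-test still counts it in the standard error, so the interval is wider than it need be. The loss depends on how strongly sex and diabetes predict titer.

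Second, the estimand and its interval are on different scales. A difference of mean log10 titers is the log of a ratio of GMTs. It does not determine the arithmetic difference that the estimand tables name.

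GMT is the summary for four of the five key secondary estimands (4.5.1, 4.5.2, 4.5.4 and 4.5.5). The first three are between-arm contrasts and carry the difference label. What is at stake is some precision and the correct naming of a reported quantity. The primary SPR analyses are not affected.

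**Working it through.** **Sample size basis.** The SAP gives no sample size for GMT, so I use the SPR basis in 2.4.1. With 75% vs 70%, a margin of 10% and one-sided alpha of 1.25% at 80% power, n = (2.2414 + 0.8416)² × (0.75×0.25 + 0.70×0.30) / (0.05 + 0.10)² = 9.505 × 0.3975 / 0.0225 = 167.9, so 168 per arm. Then 168/0.90 = 186.7, so 187. Both match the SAP.

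**Which reading of the strata wording.** SAP 5.2.1 uses the same phrase for AEs, which are to be "summarized with a two-sided 95% confidence interval in each study arm using the Wilson method, across stratification factors". A per-arm Wilson interval is ordinarily a pooled estimate, which favours the pooled reading. This is not certain: the method paper cited for the SPR analysis is titled "Stratified Wilson and Newcombe confidence intervals for multiple binomial proportions", so a stratified Wilson interval is conceivable there. That paper concerns binomial proportions and does not define a stratified t-interval.

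**Cost of pooling in the 1:1 contrasts.** Assumed inputs, none of them in the documents: within-stratum SD s = 1.0 log10, proportion female f = 0.50, proportion with diabetes d = 0.12, the two factors independent and additive, each shifting titer by e.

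- Adjusted variance: s².
- Pooled variance: s² + e²[f(1−f) + d(1−d)] = 1 + e²(0.25 + 0.1056) = 1 + 0.3556e².
- Extra width of the pooled interval: √(1 + 0.3556e²) − 1.

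| e (log10) | Pooled variance | Extra width | Range: 20–50% female, 5–20% diabetes | Range: SD 1.2 to 0.8 |
|---|---|---|---|---|
| 0 | 1.0000 | 0% | 0% | 0% |
| 0.2 | 1.0142 | 0.7% | 0.4–0.8% | 0.5–1.1% |
| 0.3 | 1.0320 | 1.6% | 0.9–1.8% | 1.1–2.5% |
| 0.5 | 1.0889 | 4.4% | 2.6–5.0% | 3.0–6.7% |

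A three-arm simulation with stratified permuted blocks (block size 6 assumed, 20,000 runs per setting, Monte Carlo SE about 0.15 percentage points) agrees. Type I error of the pooled t-test was 5.1%, 4.7%, 4.7% and 3.9% at e = 0, 0.2, 0.3 and 0.5. For the linear model with stratum terms it was 5.0%, 4.9%, 5.0% and 4.9%. Pooling is therefore conservative and does not inflate type I error.

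**Scale.** mean(log10 A) − mean(log10 B) = log10(GMT_A) − log10(GMT_B) = log10(GMT_A / GMT_B). Back-transforming the limits gives limits for the ratio.

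Take an observed ratio of 3 as an example: log10(3) = 0.477. With 168 per arm and SD 1.0, the half-width is 1.967 × √(2/168) = 0.2146. The 95% CI is 10^(0.477 ± 0.2146) = 1.83 to 4.92 (2.02 to 4.45 at SD 0.8; 1.66 to 5.43 at SD 1.2).

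The same log10 difference is an arithmetic difference of 20 mIU/mL for GMTs of 10 and 30, 200 for 100 and 300, and 2000 for 1000 and 3000. The interval therefore cannot be read as one for a difference in GMT. The null is the same on either scale, because the difference is zero exactly when the ratio is 1.

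**The case against.** The strongest reply is that nothing here is an error in a planned conclusion. A t-test on log10 titer is valid under this randomisation, the strata are not ignored because within-stratum intervals are planned, and the likely loss of precision is around 1%. The sentence on the interval itself refers to log10 titer, so a statistician would understand the difference on that scale. SAP 1.1 leaves coding descriptions to the Analysis Implementation Plan, which is not among the documents and may settle both matters. All of that stands, and it is why the point is low priority. It does not remove the point: the summary measure and the form of the contrast belong in the SAP, and Section 4 was added specifically to follow ICH E9(R1).

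Two stronger readings are tempting and should be resisted.

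- *That the unadjusted test is invalid or inflates type I error.* The calculation shows the opposite.
- *That Objective 6 has a coverage error.* That objective is "To assess SPR and GMT at weeks 4, 8, 12, and 24 between HEPLISAV-B (Arms 1 and 2 combined) and ENGERIX-B (Arm 3"), a 2:1 comparison, and the SAP does not say whether the t-test assumes equal variances. With 336 vs 168 and equal GMTs, an equal-variance test would reject 8.2% of the time at SDs of 0.8 (HEPLISAV-B) vs 1.2 (ENGERIX-B), but 2.4% with those SDs reversed and 4.9% with equal SDs. The documents favour none of these settings and do not commit to the equal-variance test. Objective 6 is not a key secondary estimand. In the 1:1 key contrasts the rate stays at 4.9% for all the unequal-SD pairs examined.

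Nor would naming an unequal-variance test give 95% coverage for the Objective 6 results actually reported. The SAP makes that analysis conditional: "where Arms 1 and 2 are combined to compare to Arm 3 (control), the analysis will occur if the directions" of the two arm differences agree. In null simulations with no stratum effect, that condition was met in 60–74% of runs. Among those runs the unequal-variance test rejected about 6.5–8.2% of the time (about 7.4% with equal SDs), against about 5% over all runs.

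**Conclusion.** The point holds as a low-priority improvement. On its most natural reading, 5.2.2 plans a pooled overall GMT contrast that is valid but slightly wider than it need be: 0% to 4.4% over stratum effects of 0 to 0.5 log10, under assumed SD, stratum mix and number evaluable. If the wording already means an adjusted contrast, that gain is nil and only the definition is missing. The scale mismatch holds on either reading: the named difference in GMT is not what the log10 t-interval estimates. It changes the label and units of the reported result, and no p-value. The Objective 6 variance question is an unstated option and does not stand as a separate error.

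**What to change.** - In 5.2.2, define the overall GMT contrast as a linear model on log10 titer with arm and the four sex-by-diabetes strata. Replace the undefined strata wording with that definition.
- Report the back-transformed GMT ratio with its 95% CI and a stated direction, for example Arm 1/Arm 3 and Arm 2/Arm 3.
- Change the label from a difference to a ratio of GMTs in 4.5.1, 4.5.2, 4.5.4, 5.2.2 and Section 6 items 11 and 13.
- Keep the within-stratum intervals as descriptive.
- Optionally, name an unequal-variance standard error (such as HC3) for the 2:1 Objective 6 contrast, without claiming 95% coverage for results that pass the same-direction condition. Stratum terms alone would not address unequal variances. HC3 is not needed in the 1:1 contrasts, where it widens the interval by about 0.8% at equal SDs.

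The cost is SAP wording and one standard model, with no new data and no change to the primary SPR analyses.

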### **Remote Data Collection**

Study visits may be conducted remotely (e.g., telephone, telehealth) in the following situations:

- A participant is unable to attend a visit because of illness, lockdown status, or quarantine; the site must inform the CMC ([contact])
- The site is temporarily unable to conduct non-essential visits in the clinic; the site must inform the CMC ([contact])

Remote visits should be conducted during the visit window according to the SOE. Regardless of the situation, sites should document which visits were conducted remotely. For visits that are conducted remotely, the site should attempt to obtain as much of the visit-specific required information based on the SOE as possible and record it on the relevant eCRF.

In addition to the remote visit, the participant should be scheduled for an in-person visit for all evaluations that were not conducted at the remote visit. If the in-person visit evaluations are outside of the visits window, have the participant in as soon as possible for safety-related evaluations as an unscheduled visit, but if within a week of the next scheduled visit window, then wait for the next scheduled visit and add any safety lab evaluations not already being performed. If the participant is unable or prefers not to come to the site for a visit, priority safety labs are permitted to be done at a local lab or as part of the standard of care. Record these on an eCRF. The priority safety labs include: chemistry, hematology, and liver function tests.

We ask the sites to prioritize sample collection for HBsAb testing at Week 12 for Arm 1 in Group A, and Week 28 for Arms 2 and 3 in Group A and for Group B. If there is a need to limit in-person interactions at the site, the in-person component can be restricted to the blood draw, and the remaining visit evaluations can be completed remotely.

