2.1.1 Group A (Non-responders, N=561)

The study is designed as an open-label three-arm study, where participants are randomized in 1:1:1 ratio to the following study arms, stratified by sex at birth (male vs. female) and diabetes diagnosis status (yes vs. no).

- Arm 1: Two doses of HEPLISAV-B at weeks 0 and 4
- Arm 2: Three doses of HEPLISAV-B at weeks 0, 4, and 24
- Arm 3: Three doses of ENGERIX-B at weeks 0, 4, and 24

Randomization will use permuted blocks and balancing by main site.

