2.4 Overview of Sample Size Considerations

2.4.1 Group A

A two-sided type I error rate is targeted at the pre-specified overall alpha level of 5% for the two primary analysis comparisons in Group A. To preserve the overall type I error rate in Group A and to allow flexible interim monitoring, a Bonferroni correction is applied, and a two-sided type I error rate of 2.5% each for the non-inferiority comparison between Arm 1 and Arm 3 and for the superiority comparison between Arm 2 and Arm 3 is allocated.

The sample size of N=187 per arm was derived as follows.

1. Non-inferiority comparison between Arms 1 and 3: For the primary objective to show that SPR proportion in Arm 1 is non-inferior to the SPR proportion in Arm 3 within the non-inferiority margin of 10%, we assume that 70% in the control arm (Arm 3) will achieve SPR. We assume the proportion of participants achieving SPR with two doses of HEPLISAV-B (Arm 1) will be higher at 75%. As a non-inferiority design, this comparison is powered to show that the SPR proportion in Arm 1 is not lower than that of Arm 3 (control) by more than the pre-specified non-inferiority margin of 10%. A sample size of 168 each in Arm 1 and Arm 3 achieves 80% power to detect a difference between the two proportions of less than 10%, in a one-sided test with type I error of 1.25% using

Page 7 of 25

normal approximation. Assuming no more than about 10% missing data for SPR, which includes loss to follow-up within each study arm prior to the primary outcome visit, the sample size is increased to 187 per study arm.

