3.2 Secondary Outcome Measures

3.2.1 Group A

- 1. HBsAb titer at the following study visits in Arm 1:
 - a. Week 4 [Secondary Objective 6]
 - b. Week 8 [Secondary Objectives 3, 5, and 6]
 - c. Week 12 [Secondary Objectives 1, 3, 5, and 6]
 - d. Week 24 [Secondary Objective 6]
 - e. Week 28 [Secondary Objectives 3 and 5]
 - f. Week 52 [Secondary Objectives 3 and 5]
 - g. Week 72 [Secondary Objective 9]
- 2. SPR defined as HBsAb ≥10 mIU/mL at the following study visits in Arm 1:
 - a. Week 4 [Secondary Objective 6]
 - b. Week 8 [Secondary Objectives 3, 5, and 6]
 - c. Week 12 [Secondary Objectives 3, 5, and 6]
 - d. Week 24 [Secondary Objective 6]
 - e. Week 28 [Secondary Objectives 3 and 5]
 - f. Week 52 [Secondary Objectives 3 and 5]
 - g. Week 72 [Secondary Objective 9]
- 3. HBsAb titer at the following study visits in Arm 2:
 - a. Week 4 [Secondary Objective 6]
 - b. Week 8 [Secondary Objective 6]
 - c. Week 12 [Secondary Objective 6]
 - d. Week 24 [Secondary Objective 6]
 - e. Week 28 [Secondary Objectives 2 and 5]
 - f. Week 32 [Secondary Objectives 4 and 5]
 - g. Week 48 [Secondary Objectives 4 and 5]
 - h. Week 72 [Secondary Objectives 4, 5, and 9]
- 4. SPR defined as HBsAb ≥10 mIU/mL at the following study visits in Arm 2:
 - a. Week 4 [Secondary Objective 6]
 - b. Week 8 [Secondary Objective 6]
 - c. Week 12 [Secondary Objective 6]
 - d. Week 24 [Secondary Objective 6]
 - e. Week 28 [Secondary Objective 5]
 - f. Week 32 [Secondary Objectives 4 and 5]
 - g. Week 48 [Secondary Objectives 4 and 5]
 - h. Week 72 [Secondary Objectives 4, 5, and 9]
- 5. HBsAb titer at the following study visits in Arm 3:
 - a. Week 4 [Secondary Objective 6]
 - b. Week 8 [Secondary Objective 6]

- c. Week 12 [Secondary Objective 6]
- d. Week 24 [Secondary Objective 6]
- e. Week 28 [Secondary Objectives 1, 2 and 3]
- f. Week 32 [Secondary Objectives 3 and 4]
- g. Week 48 [Secondary Objectives 3 and 4]
- h. Week 72 [Secondary Objectives 3 and 4]
- 6. SPR defined as HBsAb ≥10 mIU/mL at the following study visits in Arm 3:
 - a. Week 8 [Secondary Objective 6]
 - b. Week 12 [Secondary Objective 6]
 - c. Week 24 [Secondary Objective 6]
 - d. Week 28 [Secondary Objective 3]
 - e. Week 32 [Secondary Objectives 3 and 4]
 - f. Week 48 [Secondary Objectives 3 and 4]
 - g. Week 72 [Secondary Objectives 3 and 4]
- 7. Grade ≥2 AEs within 4 weeks after each injection [Secondary Objective 7]

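### The pooled HEPLISAV-B comparison (Group A Secondary Objective 6) is run only when the two arm-level differences agree in sign, a condition not supported at Weeks 4, 8 and 12

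*SAP*

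**What the plan says.** SAP 2.3.2, Group A objective 6, sets the aim: "To assess SPR and GMT at weeks 4, 8, 12, and 24 between HEPLISAV-B (Arms 1 and 2 combined") and ENGERIX-B in Arm 3.

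SAP 5.2.2 then restricts that analysis: "the analysis will occur if the directions in the outcome differences between Arm 1 and Arm 3" and between Arm 2 and Arm 3 agree. If they do not: "Otherwise, the analysis where Arms 1 and 2 are combined will not be interpretable". The condition uses only the sign of the two observed differences. It has no criterion of size, precision or heterogeneity, and no rule for ties. It is a sub-item of the antibody-titer bullet, but it speaks of outcome differences in general and names Objective 6 as an example. Objective 6 covers both SPR and GMT.

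The schedules are in SAP 2.1.1: "Arm 1: Two doses of HEPLISAV-B at weeks 0 and 4" and "Arm 2: Three doses of HEPLISAV-B at weeks 0, 4, and 24".

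SAP section 6, items 11a and 11b, lists the pooled Objective 6 estimates for GMT and SPR. It refers back to 5.2.2 without repeating the condition.

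**The concern.** Up to Week 12 the two HEPLISAV-B arms differ only in a dose that has not yet been scheduled. That is what makes pooling sensible for Objective 6. Randomised groups on the same product and doses will still fall on opposite sides of the control arm fairly often when the true difference from control is small. A sign disagreement is then weak evidence that the arms should not be combined.

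Because the condition is evaluated on the same data as the pooled estimate, it removes results selectively. Estimates near zero drop out and larger ones remain. The stake is modest: a stated secondary objective may have no pooled answer at some visits, and when the true difference is small the pooled answers that are reported run somewhat high.

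**Working it through.** **Inputs from the SAP.** Allocation is 1:1:1 (2.1.1). There are 168 evaluable participants per arm, enlarged to 187 for 10% missing data (2.4.1). Alpha is 2.5% two-sided for secondary SPR and 5% two-sided for GMT (5.2.2). The design SPR is 75% in Arm 1 and 70% in Arm 3 (2.4.1).

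**Assumed, because the SAP gives no rates for the early visits.** Arm 3 SPR of 30%, 50% or 70%; equal true response in Arms 1 and 2; normal log10 titer with equal SD.

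**Step 1: the plan's own figure.** n = (2.2414 + 0.8416)² × (0.70×0.30 + 0.75×0.25) / (0.75 − 0.70 + 0.10)² = 9.505 × 0.3975 / 0.0225 = 167.9, so 168; 168/0.9 = 186.7, so 187. Both match the SAP.

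**Step 2: chance of opposite signs with no true difference.** Let d1 = Arm 1 − Arm 3 and d2 = Arm 2 − Arm 3. Each has variance 2σ²/n, and because they share Arm 3 their covariance is σ²/n. The correlation is 0.5, so P(opposite signs) = arccos(0.5)/π = 1/3. Simulation for GMT (2,000,000 trials, 168 per arm) gives 33.4%.

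**Step 3: SPR by simulation** (1,000,000 trials per setting, 168 per arm, unstratified Newcombe 97.5% interval). Ranges run over the three Arm 3 rates. For the mean reported difference they also cover ties being run or not run.

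| True gain (points) | Opposite signs | Mean reported difference (points) |
|---|---|---|
| 0 | 28.8-29.1% (ties a further 8.5-9.3%) | not shifted |
| 5 | 15.8-18.2% (ties a further 5.6-5.7%) | 5.8-6.3 |
| 10 | 2.3-4.4% | 10.2-10.5 |
| 15 | under 0.5% | 15.0-15.1 |

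With no true difference, withheld pooled estimates average 1.3-1.5 points in absolute size, and 95% are below 3.9 points.

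**Step 4: size of the excess at 5 points.** With Arm 3 at 70% and Arms 1 and 2 at 75%, the SD of the pooled difference is √(0.21/168 + 0.1875/336) = 4.25 points. The reported mean is 5.79 (ties run) to 6.12 (ties not run), so the excess is 0.79/4.25 = 0.19 to 1.12/4.25 = 0.26 SD. Across the three rates it is 0.2-0.3 SD.

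**Step 5: GMT when a difference exists.** Withheld: 21.0% at 0.1 SD, 5.3% at 0.2 SD and 0.5% at 0.3 SD. The mean reported difference is 0.122 at a true 0.1 SD and 0.209 at a true 0.2 SD.

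**Step 6: Week 12 with the plan's 75% in both HEPLISAV-B arms.** With Arm 3 assumed at 75, 70, 65, 60 and 55%, opposite signs occur in 28.5, 15.8, 3.0, 0.2 and 0.01% of trials.

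**Step 7: error rates.** With no true difference, unconditional error stays at 2.5% for SPR and 5.0% for GMT. Among analyses that run, the same false positives are divided by a smaller count. For SPR this is 2.5/0.71 = 3.5% if ties run and 2.5/0.62 = 4.0% if not. For GMT it is 5/0.667 = 7.5%.

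**The case against.** - **Scope.** The condition sits under the titer bullet, and the SPR bullet carries no such restriction. A reader might take it as settled that SPR is covered. The text makes that likely but not explicit. If it covers GMT only, the SPR figures fall away and the GMT argument remains.
- **Rationale.** A reader might infer that the SAP blames a difference in regimen and is plainly wrong. It gives no cause for non-interpretability. The design is open-label, and incomplete or delayed series are included. The primary and key secondary antibody analyses use available data. The letter of amendment asks sites to "prioritize sample collection for HBsAb testing at Week 12 for Arm 1 in Group A, and Week 28 for Arms 2 and 3", which could leave Arm 2 with fewer Week 12 samples than Arm 1. Some caution about pooling is therefore reasonable. What does not follow is that a sign rule deals with it. Showing both arms and their numbers does so directly.
- **Error rate.** A reader might take 7.5% or 4% as an inflated type I error. It is not: the condition creates no false positives. At true SPR gains of 0 to 10 points, under 0.02% of withheld results would have excluded zero.
- **Scenarios.** The 70% control rate is for Week 28, after three ENGERIX-B doses. At Weeks 4-12 Arm 3 has been scheduled for at most two, so the gap may be wider and the condition may seldom act. This stands, and it limits the size of the problem. The simulations are also unstratified, whereas the plan stratifies its SPR intervals.
- **Information lost.** Titer and SPR by arm remain listed in SAP 3.2.1 at these visits (except Week 4 SPR in Arm 3), so a reader could approximate the pooled SPR difference. The pooled interval would still be missing.
- **Pre-specification.** It prevents ad hoc choice, but it does not stop the reported results from being selected on their own value.

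**Conclusion.** The concern holds in a limited form. At Weeks 4, 8 and 12 the direction condition is not supported by the scheduled regimens, and it makes production of the pooled result depend on that result. With equal true response in Arms 1 and 2 and no difference from Arm 3, about one third of GMT analyses would be withheld, nearly all near null. The SPR share is similar once ties are counted, if SPR is covered. The distortion matters only for true SPR differences of about 5 points or less and is negligible from 10 points up.

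These sizes rest on assumed early-visit rates and normal log titers. Week 24 is left open because the supplied text does not say whether the sample precedes Arm 2's third dose. Objective 6 is not among the key secondary estimands in SAP 4.5. The documents do not support any inference that a primary or key secondary conclusion is affected. This is a minor improvement to a secondary analysis.

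**What to change.** In SAP 5.2.2, delete the direction condition and the sentence giving its rationale. Add one sentence stating that the contrast of Arms 1 and 2 combined against Arm 3 is always reported for SPR (stratified 97.5% interval) and GMT (95% interval) at Weeks 4, 8 and 12. Include Week 24 if the sample is not taken after the third dose. Show the separate Arm 1 and Arm 2 estimates and the numbers with data beside each pooled result, so that any difference in adherence or missing data is visible. The pooled Week 4 SPR contrast also needs Arm 3's Week 4 SPR, which Objective 6 already implies but SAP 3.2.1 does not list.

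The cost is two sentences deleted, one added and one line in the outcome list. No new data are needed.
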